# **Amendment history:**

List details of all protocol amendments here whenever a new version is produced

Version Number	Date	Amendment Details
2	03.04.2023	
3	19.01.2024	
4	20.06.2024	
5	28.02.2025	

Health Research Authority (HRA) guidance has been considered when writing this protocol

# • RESEARCH REFERENCE NUMBERS

Governing body or organisation	Reference
Integrated Research Application System (IRAS)	319136
ISRCTN	
Funder's reference	NIHR132808
Research Ethics Committee (REC)	

BAY RCT: Protocol [Version 6; 25.06.2025] IRAS Project ID:319136

# **STUDY SUMMARY**

Study title	Rohavioural Activation for Vo	ung poople with depression in			
Study title	Behavioural Activation for Young people with depression in specialist child and adolescent mental health services				
Short title	BAY: Randomised Controlled Trial				
Study design	Randomised Controlled Trial with internal pilot				
Participants	Young people aged 11 to 17 y	ears with moderate to severe			
	depression				
Planned sample	446 young people				
size	51 . 14				
Treatment	Behavioural Activation will be				
duration	sessions +Treatment as Usual				
Follow-up duration	12 weeks, 6 months, and 12 m (naturalistic follow up at 12 m	•			
Planned study	4 years (45 months)	ionuisj			
period	Tycais (45 monuis)				
periou	Objectives	Outcome Measures & Data			
		Collection Tools			
Primary	Estimate the clinical and	Primary outcome measure			
	cost effectiveness of BA +	(primary endpoint 6-months			
	psychoeducation (PE) +	post-randomisation) : Mood			
	treatment as usual (TAU) on	and Feelings Questionnaire			
	depressive symptoms	(MFQ-C young person self-rated)			
	compared to PE+TAU at 6				
	months post-randomisation   Additional measures:				
	Vouth, DAMIDA Chasalina and-				
	Youth: DAWBA (baseline only), SDQ, RCADS, BADS, self-harm				
		and suicidality questions, goal-			
	based outcomes, CHU-9D, EQ-				
	5D-Y, Healthcare service use				
	schedule, Aspects of Care				
	checklist, WAI-S				
		Clinician: Session logs, End of			
		Treatment questionnaire,			
		adverse & serious adverse			
		events			
		Carer: DAWBA (baseline only),			
		MFQ, SDQ, , Carer EQ-5D-5L-			
	Childs mental health				
		PHQ-9, GAD-7- Carers mental			
		health			
		nearm			
		RA completed: Treatment as			
		usual form. Numbers discharged			
		RA completed: Treatment as usual form. Numbers discharged			

		from CAMHS; n needing therapy; (treatment as usual questionnaire & end of treatment questionnaire) Adverse & Serious Adverse Events		
Secondary	Co-design and develop our website with YP, to enhance the acceptability and effectiveness of remote delivery, and train therapists to deliver blended BA.	Feedback from young people and clinicians during development and training.		
	Conduct an internal pilot to assess recruitment and acceptability in all sites.	Progression criteria to a full trial. Collect reasons for declining. Interview participants who initially consent and then refuse to take part (early exit participants, n=15)		
	Examine immediate and longer-term acceptability, including blended delivery, potential barriers to uptake and engagement from multiple stakeholder perspectives.	Qualitative interviews with YP, carers, and clinicians End of treatment feedback forms for clinicians and YP. Website usage and engagement data		
	Use the knowledge gained, from the perspective of all stakeholders, to make recommendations for depression treatment in CAMHS, including for delivery approaches.	Recommendations to be agreed with study team and service user and carer panels, and disseminated with a broad ranging dissemination strategy		
Intervention	Blended Behavioural Activation (BA) + PE + TAU			
Comparator	Psychoeducation + TAU			
Method of delivery	Both groups will be supported by professionals based within NHS CAMHS. The intervention will be delivered using a blended approach of online and in-person behavioural activation sessions using a co-produced website, dependent on the young person's preference. BA will be delivered by Band 4 or 5 mental health professionals, depending on local service structures.			

## **Study Flowchart**

\*Internal pilot recruitment target: 176. Main trial recruitment target: 270

#### **ABBREVIATIONS**

**BA** Behavioural Activation

**CAMHS** Child and Adolescent Mental Health Services

CBT Cognitive Behavioural Therapy
CCA Cost-Consequence Analysis
CCG Clinical Commissioning Group

CEAC Cost Effectiveness Acceptability Curves
CWP Children's Wellbeing Practitioner

CYP IAPT Children and Young People's Improving Access to Psychological

**Therapies** 

DfE Department for Education

DAWBA Development and Well-Being Assessment

DHSC Department of Health & Social Care

DMEC Data Management and Ethics Committee

**GDPR** General Data Protection Regulation

**HRA** Health Research Authority

IAPT Improving Access to Psychological Therapies

ICER Incremental Cost-Effectiveness Ratio

IPT Interpersonal Therapy ITAX Intervention Taxonomy

LA Local Authorities
MAR Missing At Random

MFQ Mood and Feelings Questionnaire
MHSDS Mental Health Services Dataset
MID Minimal Important Difference
NDST Non-Directive Supportive Therapy

NICE National Institute for Health and Care Excellence

NIHR National Institute for Health Research

PPI Patient and Public Involvement
PSC Programme Steering Committee
QALY Quality-Adjusted Life Years

**RA** Research Assistant

RAG Red-Amber-Green (rating for internal pilot)

RCADS-SF25 Revised Children's Anxiety and Depression Scale (25-items)

RCI Reliable Change Index

RCT Randomised Controlled Trial
REC Research Ethics Committee
SAE Serious Adverse Event
SAP Statistical Analysis Plan

SDQ Strengths and Difficulties Questionnaire

**SOP** Standard Operating Procedure

SPA Single Point of Access
SQ Supplementary Questions
SUS Service Use Schedule

WAI-S Working Alliance Inventory Short Form

WHO World Health Organisation YP Young People/Person

YTU York Trials Unit

#### 1. BACKGROUND

Rates of emotional disorders in young people (YP) have been increasing (Sadler et al. 2018) and the covid 19 pandemic is disproportionately affecting the mental health of YP with record levels of demand (Newlove-Delgado et al. 2021; Young Minds, 2020). From 2017 to 2020, rates of probable mental health disorders in children and young people aged 7 to 16 rose from 1 in 9 (12.1%) to 1 in 6 (16.7%). Furthermore, between 2017 and 2022, rates in young people aged 17 to 19 rose from 1 in 10 (10.1%) to 1 in 4 (25.7%) (NHS, 2022). Consequently, the demand for CAMHS has continued to rise: the number of referrals of children and young people to services increased by around 77 per cent compared to before the pandemic (66,113 in February 2020 versus 37,432 in February 2022) (Plewes, 2022), and there has been a 47% increase in emergency referrals for young people under 18 to crisis care teams between December 2019 and April 2021 (Lavis, 2021). In England, it has been predicted that 1.5 million children and young people under the age of 18 will need extra mental health support as a result of the pandemic (0' Shea, 2020).

Even before the pandemic, only 25% of children and YP with mental health disorders accessed help (Office for National Statistics, 2004); those that do often have long waits for specialist therapy after assessment (Crenna-Jenning and Hutchinson, 2018; Hughes, 2019). The government Green Paper (Department for Education, 2017) offers help in schools for YP with mild to moderate problems. However, YP with more severe depression and high risk are still referred to specialist child and adolescent mental health services (CAMHS) where there is a significant shortage of skilled staff (Gilbert, 2019) and insufficient therapy skills (Lowe and Campbell, 2014; Care Quality Commission, 2019).

For some mental health services, the longest waiting times for mental health support for children and young people has been over 1 year, which significantly exceeds the UK government's goal of four weeks (Crenna-Jennings and Hutchinson, 2020). A Local Government Association report highlighted that during 2018, only 20% of young people received mental health support within 4 weeks (Local Government Association, 2022). A Care Quality Commission review found that referrals were "often" rejected due to thresholds for eligibility being too high, meaning that young people were only receiving treatment "at the point of crisis" (CQC, 2018). Due to this combination of long waiting lists and high thresholds to receive care, resources will continue to be further stretched, and young people may face an escalation in their mental health difficulties to the point of crisis before receiving support (House of Commons Health and Social Care Committee, 2021).

In response to Covid-19, delivery modes for therapy have changed with more remote working and blended therapy (Wessex Academic Health Science Network, 2020; Bhardwaj et al., 2021), which also offers an opportunity to increase access to services in the face of unprecedented demand. In response to this need, we developed a behavioural activation (BA) intervention with a brief training to clinicians without specialist therapy skills to deliver blended BA (Dubicka et al., 2021), and delivered this in a CAMHS clinic setting with young people aged 11-17 scoring 27 or above on the MFQ-C (Wood et al., 1995). Existing research demonstrates that BA is effective for adults (Stein et al., 2020) and cost effective compared to cognitive behavioural therapy (CBT) (Richards et al.,

2016). However, for YP the evidence is unclear. In developing this study, a rapid literature review was undertaken to search for relevant BA studies in depressed youths, using Psychinfo, Medline, and Cochrane reviews and trials databases (search terms: behavioural activation, depression; limits: adolescents, past 10 years, peer reviewed journals). Two systematic reviews (Martin and Oliver, 2018; Tindall et al., 2017) only found 4 small BA RCTs, with an effect size of 0.7. Only one of these, a US study (n=60) recruited YP with more severe depression, and compared BA with an active comparator; outcomes were similar with 21/27 YP completing BA no longer meeting criteria for depression (McCauley et al., 2015). In the UK, two studies in specialist CAMHS had similar findings to our feasibility work: a feasibility study and a small RCT (n=11) suggested an effectiveness signal (Pass, Lejuez and Reynolds, 2017; Kitchen et al., 2020).

# Research currently underway

The most relevant UK study that is underway is the COMBAT trial of BA in school settings (NIHR201174). However, COMBAT will recruit adolescents with mild-moderate depression with minimal complexity and risk, unlike our proposed trial in specialist CAMHS, where we will provide routine specialist clinical care to address complexity and risk management. BAY will therefore complement COMBAT, and together these studies will enable us to understand the role of BA across the spectrum of severity of depression and in different settings.

A schools study is also underway in the Netherlands (van den Heuvel et al., 2019); this is a prevention trial in high school students with elevated depressive symptoms. A number of other recently published school studies have been identified: a small UK feasibility study of BA for depressed adolescents in 5 schools demonstrated acceptability (Pass et al., 2018), and a universal prevention program in Australian primary schools found that children in the BA condition showed increased resilience at 6 months (Johnstone et al., 2020). Therefore, to our knowledge, currently there is no similar trial of BA being undertaken in specialist CAMHS recruiting adolescents with higher levels of depression severity and risk. In our feasibility studies we developed an 8 session workbook ('Be-Active') and offered BA to depressed YP in specialist CAMHS after their initial assessment (Dubicka et al., 2021). We delivered BA to YP in a development phase (n=15), and then a mixed methods feasibility study (n=36). Our BA programme showed good acceptability with YP and professionals, and relatively junior clinicians (bands 4 and 5) used it with YP with complex problems (58% had one comorbidity or more). Depression scores fell from 43.2 to 27.6, and of 8 sessions offered, YP attended a median of 8 (mean 6.6). 16 (44%) were discharged and 25 (69%) were rated as improved by clinicians. At the end of our study, during covid-19, we delivered BA remotely, with website access to the BA workbooks, and received positive feedback from families and clinicians.

# How will this research add knowledge to current NHS policy and practice

This mixed methods RCT will add much needed knowledge about BA as a first-line treatment for YP with more severe depression and risk in specialist CAMHS. NICE (NICE, 2019) recommends BA research for mild depression; we believe an RCT for those with more severe depression will provide NHS evidence about BA utility across all depression severities. Our trial will also assess the acceptability of blended delivery, which has become routine since the covid-19 pandemic (Wessex Academic Health Science Network,

2020; Bhardwaj et al., 2021), and where we have little research to inform practice. We also aim to assess the service provision implications of training clinicians with minimal therapy skills, which may have a significant impact on service delivery and optimise use of specialist therapists.

# Why is this research important and needed now?

If BA is effective and cost-effective, this could increase access to a treatment that can be delivered at scale as a first-line intervention in CAMHS. BA could free up more experienced staff and reduce waiting times for more specialist interventions, at an unprecedented time in terms of rising prevalence and demand (Sadler et al. 2018; Newlove-Delgado et al. 2021; Young Minds, 2020; Crenna-Jenning and Hutchinson, 2018; Hughes, 2019; Gilbert, 2019), and help address the profound mental health consequences of covid-19 on YP.

Even before the pandemic, rates of emotional disorders in YP were increasing (Sadler et al. 2018). The UK Millennium Cohort Study found that almost one in four girls (24%) and one in ten boys (9%) at age 14 self-reported high levels of depressive symptoms (Patalay and Fitzsimons, 2018). In their 2020 report, NHS Benchmarking noted a 15% increase in referrals to CAMHS over the past year, the highest rate of increase of any speciality in the NHS that year (Bell, 2022); this was reported to have reached an all time high in November 2020 (The Telegraph, 2021). Even more worryingly, suicide rates in YP were rising year on year before the pandemic (Bould et al., 2019). The covid-19 pandemic is further impacting on the mental health of YP, who have been disproportionately affected (Newlove-Delgado et al. 2021; Young Minds, 2020), including evidence of a rise in suicides (Disability Rights UK, 2022). Before the pandemic and subsequent increase in prevalence and demand, only 25% of children and YP with mental health disorders accessed help (Office for National Statistics, 2004), often with long waits for specialist therapy after assessment (Crenna-Jenning and Hutchinson, 2018; Hughes, 2019). In 2019, for routine cases, the average wait was 13 weeks to start treatment whilst 22% waited more than 18 weeks. Since the pandemic, the personal experience of our team suggests that increased demand and staffing challenges have continued to impact on timely access to treatment for young people.

The government Green Paper (Department for Education, 2017) offers help in schools for YP with mild and moderate problems. However, YP with more severe depression, complexity and high risk are still referred to specialist CAMHS. CAMHS have a significant shortage of skilled staff (Gilbert, 2019) to meet this demand, and the workforce is changing with employment of staff with less experience and therapy skills (Lowe and Campbell, 2014; Care Quality Commission, 2019): according to the CQC, 'the lack of availability of suitably skilled and qualified staff can mean interventions are often poorly targeted and ineffectively implemented.' YP with depression therefore need access to evidenced based psychological treatments delivered by trained staff.

Delivery modes have also changed with Covid-19 enforcing services to work remotely and offer blended therapy, taking into account patient preference, risk and needs. This way of working is likely to continue in the future to optimise access and capacity, but more research is urgently needed. Research into blended therapy for YP is limited (van der Zanden et al., 2012; Huguet et al., 2018), with some emerging evidence for adults (Ly

et al., 2015; Arjadi et al., 2018; Dahne et al., 2019) indicating effectiveness. Current NHS covid recovery protocols suggest blended approaches. An RCPsych survey (Williams et al., 2021) and a survey within our own services report that clinicians find virtual working works best once a therapeutic relationship has been established face to face. A rapid review showed both advantages and disadvantages of remote versus face-to-face work with YP, and that a personalised approach is optimal (James, 2020).

Similarly, NICE (NICE, 2019) recommends patient choice for treatment, since there is limited evidence of superiority of any particular therapy. Our HTA-funded IMPACT trial found outcomes to be similar across 3 therapies in specialist CAMHS, including a brief psychosocial intervention (BPI) that describes good clinical care; however, BPI recommends up to 16 sessions with experienced clinicians (Goodyer et al., 2017). Our BA intervention is briefer (8 sessions), and can be provided by less senior staff. Furthermore, there is evidence that therapy outcomes are similar with fewer sessions (O'Keeffe et al., 2019). BA may thus be a cost-effective first-line treatment in a stepped-care approach to YP presenting with more severe depression in CAMHS. It may also provide further patient choice, particularly as an initial alternative to antidepressants, which may not be acceptable to many YP and carers in specialist CAMHS.

In summary, if BA is effective and cost-effective, it would increase access to a treatment that can be delivered at scale in specialist CAMHS; this study would also give us information on the acceptability of different modes of delivery. BA could potentially free up more experienced staff, reduce waiting times for more specialist interventions, and provide an additional therapeutic response to the future mental health impacts of this pandemic.

#### 2. RATIONALE

There is a current lack of fully powered RCTs and economic evaluations of the use of BA interventions with YP in the UK or elsewhere to date. UK-based feasibility studies, case reports and small RCTs have demonstrated promising results. We aim to build on this research by delivering and evaluating blended BA within specialist clinical services to complement the ComBAT school BA trial (NIHR201174). We have developed, and tested through a feasibility study, a standardised BA package to be delivered online or in-person for use within CAMHS for YP experiencing more severe depression and risk. The trial aims to enable Band 4 and Band 5 mental health practitioners within NHS CAMHS services, to deliver a clinically informed intervention for YP. A fully powered RCT will evaluate its effectiveness, cost-effectiveness and acceptability compared to psychoeducation within the context of treatment as usual.

## 3. OBJECTIVES AND OUTCOME MEASURES/ENDPOINTS

#### 3.1. Aims and Objectives

The aim of the trial is to examine the effectiveness, cost-effectiveness and acceptability of blended BA + psychoeducation + treatment as usual (TAU) versus TAU + psychoeducation (PE) in newly referred depressed adolescents in specialist CAMHS.

#### 3.1.1 Primary objective

To examine the clinical effectiveness, cost-effectiveness and acceptability of BA ('Be-Active') using blended delivery, when compared to TAU+PE in depressed young people referred to specialist CAMHS at 12 weeks, 6 months (primary outcome) and 1 year follow up post randomisation (naturalistic sub-group).

# 3.1.2 Secondary objectives

- 1. Co-design and develop our website with YP, to enhance the acceptability and effectiveness of remote delivery, and train therapists to deliver blended BA.
- 2. Conduct an internal pilot to assess recruitment and acceptability in all sites, with clear progression criteria to the full trial. The pilot will include a detailed qualitative component to understand reasons why YP refused to participate, why they may have dropped-out early, and also understand potential barriers from the perspective of staff.
- 3. Examine immediate and longer-term acceptability, including blended delivery, potential barriers to uptake and engagement from multiple stakeholder perspectives.
- 4. Use the knowledge gained, from the perspective of all stakeholders, to make recommendations for depression treatment in CAMHS, including for delivery approaches.

#### 3.2. Internal Pilot

An internal pilot RCT will run for 8 months; at the end of the internal pilot, we will apply a red-amber-green (RAG) rating to assess whether the RCT can recruit and retain young people at the required rate and that it can be safely delivered within the timeframe and resources available. The criteria for a "green" rating will be:

We will aim to recruit a total of 176 participants across 5 NHS sites.

	Green	Amber	Red	Stop
Recruitment rate (Target 176)	100%	80-99%	50-79%	>50%

If the above criteria for a green rating are not met at the end of the pilot and the study is in the amber rating, the Trial Steering Committee (TSC) and the Sponsor will advise on how the risks can be mitigated, using information provided from our qualitative work.

Qualitative interviews during the internal pilot will be conducted with participants who consent to the trial, are allocated to BA and engage with their treatment, as well as those who do not begin treatment. This will be used to help inform recruitment and retention for the main trial.

Green: 100% randomisation, continue the trial.

Amber: 80-99% - 80% of target is 4.4 participants per site per month (80% total per site = 141). This would need 6 young people recruited per site per month for the remaining 16 months of the trial. Recruitment procedures will be reviewed, and strategies developed to address problems, including recruiting additional clinics; review in 6 months by the TSC/DMC/TMG. Consideration will be given to recruiting an additional site, as well as increasing clinics within existing sites.

Red: 50-79% - 50% target is 2.75 per site per month (50% total per site = 88). This would need 6.9 participants recruited per site per month for the remaining 16 months of the study. In addition to maximising the number of clinics for recruitment in each site, we will approach neighbouring trusts at each site. There will be close monitoring over 6 months by the TMG/TSC/DMC to assess progress and recruitment and retention strategies. Stop

Stop: in consultation with the funder we will consider close down of the trial.

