#### 7. STUDY PROCEDURES

#### 7.1. Recruitment

We will recruit participants through NHS CAMHS. CAMHS sites within 5 NHS Trusts will be invited to both promote the RCT and assist with identifying young people who may be suitable and interested in participating. BAY research team members will work closely with members of the CAMHS team to ensure that the professionals understand the study and its inclusion criteria. The study will be embedded within the CAMHS team to ensure all potential participants are aware of the opportunity. There will be 3 methods of recruitment through the CAMHS service: 1) Identification by clinician, 2) MDT Meetings, and 3) Screening records

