#### 9. STATISTICAL AND DATA ANALYSIS

# 9.1 Sample Size

For 90% power to detect an effect size of 0.3125 we will require 8 groups of 28 in the intervention arm and 224 individuals in the control arm, giving a total of 448 participants. This effect size corresponds to a minimally important difference of 5 points on the MFQ-C(Wood et al., 1995) with a standard deviation of 15. This calculation was performed in Stata using the 'clsampsi' command and includes a baseline-follow up correlation of 0.41 and an ICC of 0.01 in the intervention arm. Parameter estimates were informed by our feasibility study and previous IMPACT trial (Goodyer et al., 2017; Goodyer et al., 2007,). 7% attrition was observed at 6 months in the HTA ADAPT trial and 16% in IMPACT, however this was at 18 months. Conservatively inflating the current sample size by 15%, we will recruit a total sample size of 528.

On 28th April 2025the funder approved a request from the study team for a costed extension, under the condition that the sample size be recalculated to provide 80% power. Assuming based on the trial data collected so far an updated baseline-follow-up correlation of 0.45, 13 groups of 12 participants in the intervention arm, a 70% retention rate, an effect size of 0.30 and keeping all other parameters the same, 446 participants (223 per group) are required for 80% power to detect a minimum clinically important difference of five points on the MFQ-C.

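### The internal pilot's Stop band has its sign reversed, and its per-site and catch-up recruitment rates fit four sites rather than the stated five

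*Protocol*

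**What the plan says.** Section 3.2 gives the pilot's length ("An internal pilot RCT will run for 8 months") and its target ("We will aim to recruit a total of 176 participants across 5 NHS sites"). Section 7.1 agrees on the number of sites: "CAMHS sites within 5 NHS Trusts will be invited".

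The table in Section 3.2 rates recruitment as a percentage of 176: Green 100%, Amber 80-99%, Red 50-79%, and Stop printed as >50%. The text then turns two of the bands into site rates and totals:

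- Amber: "80% of target is 4.4 participants per site per month (80% total per site = 141"), followed by "This would need 6 young people recruited per site per month for the remaining 16 months of the trial".
- Red: "Red: 50-79% - 50% target is 2.75 per site per month (50% total per site = 88"), followed by "This would need 6.9 participants recruited per site per month for the remaining 16 months of the study".

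The paragraph on Stop gives no figure; it says only that closing the trial would be considered with the funder.

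The current sample size is in Section 9.1: "446 participants (223 per group) are required for 80% power". The note under the study flowchart splits it into 176 for the pilot and 270 for the main trial. The figure of 528 appears only in Section 9.1, as the total that the 2025 recalculation replaced.

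**The concern.** Two things stand out. First, the bands descend from 100% to 50%, and the last one then points upwards. Taken literally, every Green and Amber result and nearly all of Red also meets Stop, while recruitment below half the target has no rating.

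Second, the site rates do not follow from the target, site count and duration given in the same section. Section 3.1.2 promises clear progression criteria. A committee that used the site rates as a working guide would be reading from figures that disagree with the percentages beside them. The catch-up rates tell the steering committee and the funder how hard each site must recruit after a shortfall, and so bear on whether to add clinics or sites.

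**Working it through.** **Inputs.** Pilot target 176, 5 sites, 8 months, and 16 months remaining after the pilot (Section 3.2). Totals of 528 (superseded) and 446 (current) from Section 9.1.

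**Band totals.** 0.80 x 176 = 140.8, rounded to 141; 0.50 x 176 = 88. The printed totals are right, but they are totals over all sites. Per site, with 5 sites, they are 140.8/5 = 28.2 and 88/5 = 17.6.

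**Site rates.** Rate = fraction x 176 / (sites x 8 months).

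| Sites | 100% | 80% | 50% |
|---|---|---|---|
| 4 | 176/32 = 5.50 | 140.8/32 = 4.40 | 88/32 = 2.75 |
| 5 (stated) | 176/40 = 4.40 | 140.8/40 = 3.52 | 88/40 = 2.20 |
| 6 | 176/48 = 3.67 | 140.8/48 = 2.93 | 88/48 = 1.83 |

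The printed 4.4 and 2.75 are reproduced exactly with 4 sites. With 5 sites, 4.4 is the full target rate. The excess is 4.40/3.52 = 1.25 and 2.75/2.20 = 1.25, so 25% in both cases. Rounding cannot explain it. Keeping 5 sites would instead need a pilot of about 6.4 months (141/(5 x 4.4) = 6.41; 88/(5 x 2.75) = 6.40), against the stated 8.

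**Catch-up rates.** Rate = (N - recruited so far) / (sites x 16 months).

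| Sites | N | From 141 | From 88 |
|---|---|---|---|
| 4 | 528 | 387/64 = 6.05 | 440/64 = 6.88 |
| 4 | 446 | 305/64 = 4.77 | 358/64 = 5.59 |
| 5 | 528 | 387/80 = 4.84 | 440/80 = 5.50 |
| 5 | 446 | 305/80 = 3.81 | 358/80 = 4.48 |
| 6 | 528 | 387/96 = 4.03 | 440/96 = 4.58 |

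Only 4 sites with 528 gives the printed 6 and 6.9. Holding the total at 528 and correcting only the site count, the printed figures are about 25% too high (6.05/4.84 = 1.25; 6.88/5.50 = 1.25).

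**Which total the 16 months belongs to.** 176/528 is one third, and 8 of 8 + 16 = 24 months is also one third. At 5 sites the even rate for 528 is 528/(5 x 24) = 4.4, the same as the pilot's 100% rate. So the 16-month schedule fits the 528 plan. It was not evidently rebuilt for 446.

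**Stop band.** Green, Amber and Red cover 50% upwards. The only part of the scale left is below 50%.

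**The case against.** The strongest defence is that the rating rests on the percentage of one overall target. The table heads the row with the target of 176, and the text repeats the percentage bands. The site rates only translate those bands, and nothing says that a rating is assigned by site rate. This stands. A reader might infer that the same recruitment could earn two ratings: for example, that 2.5 per site per month at 5 sites, below the printed 2.75, would count as Stop. It would not: 2.5 x 5 x 8 = 100 recruits, which is 57% of 176 and so Red in both the table and the text.

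It can also be said that the Stop sign will mislead nobody, since <50% is the only coherent reading and stopping is not automatic. That is fair as to consequence. But no other text in the protocol corrects the sign, and less-than signs are printed properly elsewhere (the session counts in Sections 10.2 and 10.3).

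Third, the decision is probably past. The protocol is Version 6 of June 2025, Section 9.1 reports a funder decision of April 2025 and uses data already collected, and Section 7.3 ties 12-month follow-up to recruitment before July 2024. The document does not state that the pilot has ended, but it very likely has.

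Finally, a reader might set the printed catch-up rates against 446 and call them 54-57% too high (6.9/4.48 = 1.54; 6/3.81 = 1.57). That mixes a target set in 2025 with a 16-month schedule that fits 528. On a common total the error is about 25%, the same discrepancy in site count as in the threshold rates.

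**Conclusion.** Section 3.2 is wrong as written in four places: the Stop sign; the site rates (25% too high for the stated 5 sites); the per-site label on 141 and 88; and the catch-up rates (about 25% too high at 5 sites with 528, and not updated to the current total). The Green, Amber and Red percentages and the counts 176, 141 and 88 are correct, so a rating by total recruitment stands, apart from the Stop sign.

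The result rests on the stated 5 sites, 8 months and 16 months. If the pilot in fact ran with 4 sites, the printed threshold rates are right and the site count is what needs changing. That the figures were carried over from a four-site plan is an inference from the arithmetic; the protocol does not say so. Nor does anything in it show that a wrong threshold was applied. The randomisation, the primary analysis and the current sample size are not affected.

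**What to change.** - In the table, print Stop as <50%.
- Label 141 and 88 as totals across all sites.
- Restate the site rates as 3.5 (80%) and 2.2 (50%) per site per month for 5 sites, or state the site count actually used.
- Restate the catch-up rates for the stated site count, with the target and remaining months they assume: 4.8 and 5.5 for 528 over 16 months at 5 sites. For 446 they would be 3.8 and 4.5, but only if 16 months still holds, which must be checked after the costed extension.
- If the pilot decision has been taken, record which thresholds were applied and against which total.

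The cost is wording in one table and two paragraphs, plus a short note on the decision. Design, conduct and analysis do not change.
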